3. The following organisms will be considered pathogens if grown from urine culture at $\geq 10^5$ CFU/mL if obtained via a newly placed catheter or at $\geq 10^4$ CFU/mL if obtained via suprapubic aspiration, new nephrostomy or cystoscopy. They will not be considered pathogens when grown from urine culture if obtained via midstream clean catch or a disinfected collection port. They will also not be considered pathogens when grown from blood cultures, unless simultaneously grown from urine culture at $\geq 10^5$ CFU/mL if

obtained via a newly placed catheter or at $\geq 10^4$ CFU/mL if obtained via suprapubic aspiration, new nephrostomy or cystoscopy:

- Coagulase negative staphylococci, including:
 - *Staphylococcus epidermidis*
 - *Staphylococcus hominis*
 - *Staphylococcus haemolyticus*
 - *Staphylococcus simulans*
 - *Staphylococcus capitis*
 - *Staphylococcus warneri*
 - *Bacillus* spp. (other than *B. anthracis*)
4. The following organisms will be considered non-susceptible to eravacycline or comparator and will NOT be analyzed as pathogens:
- *Pseudomonas* spp.
 - Yeast and fungi
5. Pathogens for MRC review: isolates will be reviewed in a blinded manner by the MRC on a case-by-case basis if none of rules 1 through 3 above apply.

If more than 1 suitable urine culture specimen is obtained prior to the first dose of study drug therapy, and the same pathogen is isolated, the one with the highest MIC to study drug will be utilized in all analyses and the highest colony count will be used. If pathogens have the same MIC to study drug, the pathogens will be considered equivalent and a representative isolate will be selected from among them based on the lowest central laboratory accession number and the highest colony count will be used.

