3.2. Evaluability Review

3.2.1. Membership and Responsibilities

The MRC will be responsible for reviewing microbiological data, including pathogen determination, as outlined in the Microbiological Outcomes Review Plan. The Evaluability Review Committee (ERC) will review clinical and microbiological data to assess inclusion in or exclusion from the CE populations as outlined in the Clinical Evaluability Review Plan. MRC and ERC members will be blinded to treatment assignment and will review the data concurrent with the conduct of the study. Final pathogen determinations and inclusion in analysis populations will be determined prior to database lock except for those criteria which require unblinded data (for example, determination of whether or not the subject received the study drug to which s/he was randomized).

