5.4. Baseline Microbiology

The microbiological assessment of the baseline blood and urine specimens will be summarized by treatment group for the micro-ITT, micro-MITT and ME-TOC populations. The number and percentage of subjects with a suitable urine specimen obtained, the number of isolates obtained and whether or not the culture was interpretable will be summarized by treatment group. The distribution of the urine collection methods will also be presented.

The pathogenic organisms identified from the baseline blood culture or urine culture specimens will be presented. The number and percentage of subjects with gram-negative organisms (aerobes), overall and within Enterobacteriaceae and non-Enterobacteriaceae, gram-positive organisms (aerobes) and all anaerobes will be presented by genus and species for the micro-ITT, micro-MITT and ME-TOC populations overall and by primary site of infection (pyelonephritis and normal urinary tract anatomy vs. all other diagnoses). The same pathogen identified from both the blood and the urine culture will be counted only once in the summary. The pathogenic organisms identified at baseline from a blood sample will also be presented separately for the micro-ITT population, micro-MITT and ME-TOC populations. The number and percentage of subjects with levofloxacin resistant and ertapenem resistant organisms will also be presented. The number and percentage of subjects with monomicrobial (gram-negative aerobe, gram-positive aerobe, anaerobe) and poly-microbial infections (gram-negative aerobes only, gram-positive aerobes only, anaerobes only, gram-negative aerobe and anaerobe, gram-positive aerobe and anaerobe, gram-negative and gram-positive aerobe, and gram-negative aerobe, gram-positive aerobe and anaerobe) will be provided for specimens from the blood or urine culture.

Several tables providing the frequency distribution of the minimum inhibitory concentrations (MIC) by pathogen as reported by the central laboratory will be provided for the micro-ITT, micro-MITT and ME-TOC populations:

- The MIC distribution to eravacycline of the baseline pathogens.
- The MIC distribution to ertapenem of the baseline pathogens.
- The MIC distribution to levofloxacin of the baseline pathogens.
- The MIC distribution to the study drug received of the baseline pathogens. For those subjects who received the wrong study drug, the summary will be based on actual treatment received.

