5.6. Study Drug Exposure and Compliance

Exposure to study drug (IV and oral) will be characterized by the total duration of treatment (IV and oral), duration of IV treatment, the number of infusion days, the number of active doses (IV only), total IV dose received, the average daily dose over all infusion days, duration of PO treatment, and the number of PO days. Descriptive statistics for each measure of exposure to study drug will be summarized by treatment group for Safety, micro-ITT, and micro-MITT populations.

Duration of treatment is defined as the number of days from when the subject first received study treatment until the day that they last received study treatment and is calculated as (date of last dose – date of first dose +1). Total duration of treatment (IV and PO), Duration of IV treatment and Duration of PO treatment will be calculated separately.

An infusion day is the 24-hour period during which the full daily dose of study drug is to be administered. An infusion day can be coincidental with a calendar day or can start in the afternoon of 1 day and complete in the morning of the next day.

Number of PO days would be calculated as:

$$\text{Number of PO days} = [\text{Duration of PO days} - \text{Number of days dose was missed}]$$

Study drug (IV only) is administered in mg/kg for the eravacycline arm and in g for theertapenem arm. Actual daily dose in mg is dependent on the treatment received, weight (in the case of eravacycline), the volume of drug administered (recorded on the eCRF), and the volume of drug prepared (recorded on the eCRF), as follows:

For eravacycline:

$$\text{actual daily dose (mg)} = 1.5 * \text{weight (kg)} * (\text{total volume of drug administered for dose}) / (\text{total volume of drug prepared for dose})$$

For ertapenem:

actual daily dose (mg) = $1000 * (\text{total volume of drug administered for dose}) / (\text{total volume of drug prepared for dose})$

The average daily dose of eravacycline, expressed as mg and as mg/kg, is based on the dose of active drug per infusion day, as follows:

average daily dose (mg) = $\Sigma \text{actual daily dose (mg) eravacycline over all doses} / \text{number of infusion days}$

average daily dose (mg/kg) = $\text{average daily dose (mg)} / \text{screening weight (kg)}$

It is expected that the average daily dose of eravacycline will be approximately 1.5 mg/kg.

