5.7.3.2. Responder Outcome in Subjects with and without Levofloxacin-Resistant Baseline Pathogens

Responder outcome will be analyzed at the EOI and TOC visits in subjects with levofloxacin-resistant baseline pathogens. A 2-sided 95% CI for the observed difference in the responder rate at the EOI and TOC visits will be calculated for the micro-ITT population using the same method as for the primary efficacy analysis.

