5.7.3.3. Responder Outcome in Subjects with and without Ertapenem-Resistant Baseline Pathogens

Responder outcome will be analyzed at the EOI and TOC visits in subjects with ertapenem-resistant baseline pathogens. A 2-sided 95% CI for the observed difference in the responder rate at the EOI and TOC visits will be calculated for the micro-ITT population using the same method as for the primary efficacy analysis.

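### Duplicate baseline isolates are chosen by highest MIC to an arm-specific drug, so the drug-common MIC tables and the ertapenem-resistance flag depend on the assigned arm

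*SAP*

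**What the plan says.** SAP 3.1.4 covers this case: "If more than 1 suitable urine culture specimen is obtained prior to the first dose of study drug therapy, and the same pathogen is isolated". Its rule is that "the one with the highest MIC to study drug will be utilized in all analyses". If the MICs tie, "a representative isolate will be selected from among them based on the lowest central laboratory accession number". In either case the highest colony count is used.

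Section 3.1.4 does not define study drug. SAP 5.6 uses the term by arm: "Study drug (IV only) is administered in mg/kg for the eravacycline arm and in g for" the ertapenem arm. SAP 5.4 and 5.7.3.5 refer in places to the study drug received; 3.1.4 does not say whether it means the drug randomised or the drug received.

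The kept isolate feeds several outputs:

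- SAP 5.4 tabulates MICs to eravacycline, ertapenem and levofloxacin for all baseline pathogens (for example "The MIC distribution to eravacycline of the baseline pathogens") and counts subjects with levofloxacin- and ertapenem-resistant organisms. SAP 4.2 presents all tables by treatment.
- SAP 5.7.3.3: "Responder outcome will be analyzed at the EOI and TOC visits in subjects with ertapenem-resistant baseline pathogens".
- SAP 5.7.3.2: "Responder outcome will be analyzed at the EOI and TOC visits in subjects with levofloxacin-resistant baseline pathogens".
- SAP 5.7.3.5 reports per-pathogen response for resistant organisms.

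**The concern.** A baseline characteristic should be the same whichever arm the patient draws. Under this rule, two patients with identical pairs of isolates can receive different baseline MICs and different resistance flags because of randomisation alone. A subgroup whose membership depends on the arm no longer gives a randomised comparison. A baseline table meant to show that the arms are alike can show a difference that the rule itself created.

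At stake are the drug-common MIC tables, the ertapenem-resistant counts, the responder comparison at EOI and TOC in ertapenem-resistant subjects, and the per-pathogen results for ertapenem-resistant organisms. The levofloxacin flag has a related weakness: it is read from an isolate that neither arm chose on levofloxacin MIC. The documents give no basis for saying which way that would push the comparison.

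**Working it through.** **The plan's own figure.** There is none for duplicate specimens or discordant MICs. The only planning figure used here is the micro-ITT size, 395 per arm (SAP 4.1). It reproduces: (1.960 + 0.842)² × (0.71 × 0.29 + 0.72 × 0.28) / (0.10 − 0.01)² = 7.849 × 0.4075 / 0.0081 = 394.9, so 395.

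**Tracing one pair.** Let isolates A and B be the same species from two pre-dose specimens. A is ertapenem-resistant with the lower eravacycline MIC. B is ertapenem-susceptible with the higher eravacycline MIC. Randomised to ertapenem, the patient keeps A and is flagged resistant. Randomised to eravacycline, the patient keeps B and is not.

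Such pairs are plausible. Protocol 7.2 gives eravacycline MIC50/90 for *K. pneumoniae* as 0.5/1 µg/mL overall and 0.5/2 µg/mL in carbapenem-resistant isolates. Eravacycline MIC is therefore a weak guide to which of two isolates is carbapenem-resistant.

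**Excess resistant labels.** Two inputs are assumed, not taken from the documents:

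- f, the share of micro-ITT subjects with duplicate specimens growing the same pathogen: 5-15%.
- q, the share of those pairs that differ in ertapenem category: 5-10%.

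In the ertapenem arm every such pair is labelled resistant. Under the eravacycline-arm rule about half would be, if the two MICs are unrelated. Excess = 395 × f × q × 0.5.

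| f | q | Excess labels |
|---|---|---|
| 5% | 5% | 0.49 |
| 5% | 10% | 0.99 |
| 15% | 5% | 1.48 |
| 15% | 10% | 2.96 |

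If the two MICs always rank the isolates alike, the excess is 0. If they always rank them in opposite order, the factor 0.5 becomes 1 and the range doubles, to 0.99-5.9. With wider assumptions and unrelated MICs, the excess runs from 0.1 (f = 1%, q = 5%) to 7.9 (f = 20%, q = 20%).

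**A limit on q.** Two isolates cannot differ in category more often than twice the per-isolate prevalence of resistance. If 2% of isolates are resistant (assumed) and subjects with duplicates are typical, q is at most 4%. The excess is then at most 395 × 0.05 × 0.04 × 0.5 = 0.4 to 395 × 0.15 × 0.04 × 0.5 = 1.2. The subgroup would be about 395 × 0.02 = 8 per arm, so this is roughly 5-15% of it.

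**Shift in the drug-common MIC tables.** Assume a within-pair SD of 1 dilution on the log2 scale. The higher of two values exceeds the mean by 1/√π = 0.56 dilution. In duplicate pairs, the kept isolate's eravacycline MIC is therefore raised by 0.56 in the eravacycline arm. In the ertapenem arm it is raised by 0.56 times the between-drug correlation; simulation gave 0.00, 0.28 and 0.51 at correlations 0, 0.5 and 0.9. Over a whole arm the gap is diluted by f: at correlation 0.5, (0.56 − 0.28) × 0.05 to × 0.15 = 0.01 to 0.04 dilution.

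**The case against.** The strongest reply is that the rule touches only subjects with duplicate, MIC-discordant isolates, that nothing confirmatory rests on it, and that four stronger readings fail. Most of this stands.

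- **Primary analysis.** A reader might infer that micro-ITT entry becomes arm-dependent through an ertapenem breakpoint. The SAP sets no such breakpoint. Section 3.1.4 removes only *Pseudomonas*, yeast and fungi as non-susceptible, and 5.7.3.3 analyses ertapenem-resistant subjects within micro-ITT. The duplicate rule applies only when the pathogen is the same, so identity is unchanged, and microbiological response rests on culture results for that pathogen and its colony count, not on MIC.
- **Blinding.** SAP 3.2.1 says "Final pathogen determinations and inclusion in analysis populations will be determined prior to database lock", and SAP 2 delivers treatment codes only after lock. That could be read as a conflict. But 3.2.1 goes on to exempt criteria that need unblinded data, and the pathogen-review inputs named in 3.2.2 do not include MIC. The selection is deterministic with a tie-break, so it can be programmed in advance and leaves no discretion.
- **Resistance emergence.** Decreasing susceptibility (5.7.3.5) is measured against the drug received. Under the arm-specific reading, starting from the highest baseline MIC to that drug is coherent and conservative in both arms. A false rise confined to the ertapenem arm could appear only if study drug meant eravacycline for everyone, and on that reading the arm dependence disappears. The two faults cannot be claimed together.
- **All MIC tables.** Tables by MIC to the study drug received are arm-specific by design and are not at fault.

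Duplicates also cannot be presumed common. Using routine-care specimens is permitted, but they may simply stand in for the screening culture. None of this removes the arm dependence of the drug-common tables and the ertapenem-resistance flag.

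**Conclusion.** The point holds as a minor one. As written, the rule makes the drug-common baseline MIC tables and the ertapenem-resistant counts, subgroup and per-pathogen results depend on assigned arm in subjects with duplicate, MIC-discordant isolates. The levofloxacin flag rests on an isolate not chosen for that drug, with no known direction of bias.

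On assumed rates the effect is about 0.5 to 3 excess ertapenem-resistant labels among 395 subjects. It is lower if resistance is rare and zero if the two MICs agree in rank. That is negligible for the trial as a whole and noticeable only if the resistant subgroup is small. The resistance subgroups are additional analyses with no decision rule attached. The conclusion that the arms are treated differently rests on the SAP's arm-specific use of study drug, which 3.1.4 does not override. The size rests wholly on assumption.

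**What to change.** Replace the selection rule in SAP 3.1.4 with:

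*For each baseline pathogen, the highest MIC to each drug (eravacycline, ertapenem, levofloxacin) among duplicate baseline isolates is used for that drug's tables, resistance flags and baseline for decreasing susceptibility, in both arms. Where a single representative isolate per pathogen is needed, it is the one with the lowest central laboratory accession number. The highest colony count is used.*

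Apply it before database lock. The artificial between-arm difference is then zero by construction, no treatment code is needed, and the question of drug randomised versus drug received no longer arises for the selection. The conservative baseline for decreasing susceptibility is kept.

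The cost is one short SAP edit and a small programming change. SAP 5.4 already calls for MICs to all three drugs, so no new data are required.

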3.1.5. Modified Microbiological Intent-to-Treat (Micro-MITT) Population

The micro-MITT population will consist of all subjects in the micro-ITT population who receive at least 1 dose of study drug. Analyses in this population will be presented in summary tables by the treatment arm to which the subject was randomized.

3.1.6. Clinically Evaluable (CE) Populations

Five CE populations will be defined: the CE-Day 5, CE-EOI, CE-EOT, CE-TOC and CE-FU. Subjects will be included in or excluded from the CE populations based on the criteria listed below:

1. Minimal Disease Criteria:

Minimal disease is defined as meeting all of the following inclusion criteria:

- Inclusion criterion 1: Male and female subjects with either:
 - a. Pyelonephritis and normal urinary tract anatomy (approximately 50% of the total population), OR

- b. cUTI with at least 1 of the following conditions associated with a risk for developing cUTI:
 - i. Indwelling urinary catheter
 - ii. Urinary retention (at least approximately 100 mL of residual urine after voiding)
 - iii. History of neurogenic bladder
 - iv. Partial obstructive uropathy (eg, nephrolithiasis, bladder stones, and ureteral strictures)
 - v. Azotemia of renal origin (not Congestive Heart Failure (CHF) or volume related) such that the serum blood urea nitrogen (BUN) is elevated (> 20 mg/dL) AND the serum BUN: creatinine ratio is < 15
 - vi. Surgically modified or abnormal urinary tract anatomy (eg, bladder diverticula, redundant urine collection system, etc) EXCEPT surgery within the last month (placing of stents or catheters is not considered to be surgical modification)
 - Inclusion criterion 4: At least 2 of the following signs or symptoms:
 - a. Chills, rigors, or warmth associated with fever (oral, rectal, tympanic, or by temporal artery temperature $> 100.4^{\circ}\text{F} / 38^{\circ}\text{C}$) or hypothermia (oral, rectal, tympanic, or by temporal artery temperature $< 95^{\circ}\text{F} / 35^{\circ}\text{C}$)
 - b. Flank pain (pyelonephritis) or pelvic pain (cUTI)
 - c. Nausea or vomiting
 - d. Dysuria, urinary frequency, or urinary urgency
 - e. Costo-vertebral angle tenderness on physical examination
 - Inclusion criterion 5: Urine specimen with evidence of pyuria:
 - a. Dipstick analysis positive for leukocyte esterase, OR
 - b. ≥ 10 white blood cells per cubic millimeter, OR
 - c. ≥ 10 white blood cells per high power field
2. Prior Antibiotic Therapy:

Subjects who receive only a single dose of effective non-study antibiotics in the 72 hours prior to randomization can be enrolled in the study. Subjects who receive more than a single dose of effective non-study antibiotics in the 72 hours prior to randomization will be excluded from the CE populations.

3. Concomitant Antibiotic Therapy:

Subjects who receive any systemic concomitant antibiotic therapy from the first dose of study drug through the Day 5 Visit (CE-Day 5 population), EOI Visit (CE-EOI population), EOT Visit (CE-EOT population), TOC Visit (CE-TOC population) and FU Visit (CE-FU population) that is potentially effective against the baseline pathogen will be excluded from the CE populations with the following exceptions:

- The subject is a clinical failure at Day 5 (CE-Day 5 population), EOI (CE-EOI population), EOT (CE-EOT population), TOC (CE-TOC population) or FU (CE-FU population) and received non-study antibiotics for insufficient therapeutic effect of the study drug
- The subject received an oral antibiotic with no systemic absorption

Subjects who do not have a pathogen isolated at baseline and receive an antibiotic with expected activity against cUTI pathogens will also be excluded from the CE populations unless considered a failure by the Investigator at Day 5, EOI, EOT, TOC or FU and received non-study antibiotics for insufficient therapeutic effect of the study drug. Subjects who receive a systemic concomitant antibiotic that is not effective against the baseline pathogen, or if no pathogen is isolated and the antibiotic does not have activity against cUTI pathogens, will be included in the CE populations.

4. Study Drug Therapy:

Subjects must meet all of the following to be included in the CE populations:

- Received the correct study drug based on the randomization assignment for the entire treatment period
- Study personnel involved in the assessment of efficacy or monitoring efficacy data remained blinded to treatment assignment, unless a treatment limiting AE occurred which required unblinding
- The subject received at least 3 days of study drug
- The subject was at least 80% compliant with study drug

5. Clinical Outcome Assessment:

Subjects must meet the following to be included in the CE populations:

- For the CE-Day 5 population:
 - Completed the Investigator's assessment of clinical response (ie, was not deemed an indeterminate outcome) at the Day 5 Visit
 - The Day 5 Visit occurred 4-6 days following randomization
- For the CE-EOI population:
 - Completed the Investigator's assessment of clinical response (ie, was not deemed an indeterminate outcome) at the EOI Visit

- The EOI Visit occurred within 1 day of the last dose of IV study drug
- For the CE-EOT population:
 - Completed the Investigator's assessment of clinical response (ie, was not deemed an indeterminate outcome) at the EOT Visit
 - The EOT Visit occurred within 1 day of the last dose of study drug (IV or PO)
- For the CE-TOC population:
 - Completed the Investigator's assessment of clinical response (ie, was not deemed an indeterminate outcome) at the TOC Visit, unless the patient was defined as a clinical failure at the EOT Visit
 - The TOC Visit occurred 13-18 days following randomization and at least 5 days following the last dose of study drug, unless the subject was considered to be a clinical failure based on the Investigator's assessment at the EOT Visit
- For the CE-FU population:
 - Completed the Investigator's assessment of clinical response (ie, was not deemed an indeterminate outcome) at the FU Visit, unless the patient was defined as a clinical failure at the EOT or TOC Visits.
 - The FU Visit occurred 20-29 days following randomization, unless the subject was considered to be a clinical failure based on the Investigator's assessment at the EOT or TOC Visits.

6. Baseline or Inter-Current Medical Events:

Subjects will be excluded from the CE populations if the Investigator has documented in the eCRF that they meet any 1 of the following protocol-defined exclusion criteria at baseline (ie, prior to randomization):

- Exclusion criterion 2: History of an ertapenem-resistant urinary tract infections within 1 year of consent
- Exclusion criterion 3: Likely to require > 10 days of antibiotic treatment to cure the acute cUTI or likely to receive ongoing antibacterial drug prophylaxis prior to the FU visit (eg, subjects with vesiculo-ureteral reflux)
- Exclusion criterion 6: Complicated pyelonephritis with complete obstruction or known or suspected renal or perinephric abscess, emphysematous pyelonephritis, OR Any condition likely to require surgery to achieve cure (this does NOT include procedure to place catheters or obtain diagnosis)
- Exclusion 7: Known or suspected fungal infection
- Exclusion 8: Uncomplicated lower urinary tract infection

- Exclusion 9: Suspected or confirmed active prostatitis, or currently under treatment for prostatitis
- Exclusion 10: Subjects with high risk for cUTI due to *Pseudomonas* sp. (eg, History of prior cUTIs due to *Pseudomonas*, ≥ 20 mg QD prednisone or equivalent steroid, and other risk factors as perceived by the investigator)

